8.6 Duration of Therapy

Treatment with durvalumab will continue for 1 month taken from date of first infusion irrespective of treatment omissions.

8.7 Patient Compliance

Trained medical personnel will administer durvalumab. Treatment compliance will be monitored by drug accountability, as well as recording durvalumab administration in the patient's medical record and case report form (CRF).

8.8 Concomitant Therapy

8.8.1 Permitted

- Concomitant medications or treatments (e.g. acetaminophen, diphenhydramine) deemed necessary to provide adequate prophylactic or supportive care except for those medications identified as "excluded" as listed in Section 7.8.2.
- Use of immunosuppressive medications for the management of acute immune related adverse events as outlined in Section 7.5 is acceptable. In addition, intranasal/inhaled corticosteroids or systemic steroids that do not to exceed 10 mg/day of prednisone or equivalent dose of an alternative corticosteroid are permissible.

8.8.2 Not Permitted

- The chronic use of immunosuppressive medications including, but not limited to systemic corticosteroids at doses beyond 10 mg/day of prednisone or equivalent, methotrexate, azathioprine, and tumour necrosis factor alpha blockers.
- Live attenuated vaccines within 30 days of dosing with study agent. Inactivated viruses such as those in the influenza vaccine are permitted.

Prohibited and Rescue Medications	
Rescue/supportive medication/class of drug:	Usage:
Concomitant medications or treatments (eg, acetaminophen or diphenhydramine) deemed necessary by the Investigator to provide adequate prophylactic or supportive care, except for those medications identified as “prohibited” as listed above	To be administered as prescribed by the Investigator
Best supportive care (including antibiotics, nutritional support, growth factor support, correction of metabolic disorders, optimal symptom control, and pain management [including palliative radiotherapy, etc])	Should be used when necessary for all patients

- Concurrent administration with other anti-cancer therapy, radiation therapy or investigational treatment.

Blood donation

Subjects should not donate blood while participating in this study and for at least 90 days following the last infusion of durvalumab.

9 EVALUATION DURING AND AFTER PROTOCOL TREATMENT

All patients entered on study must be evaluated according to the schedule outlined in Appendix I.

9.1 Evaluation during Protocol Treatment

Investigations		Timing
Physical Exam including:	
 physical examination including blood pressure performance status Concomitant medication 	Prior to each infusion until off protocol therapy.
Hematology ¹	
 CBC including haemoglobin, differential leukocyte, platelet count 	Prior to each infusion until off protocol therapy.
Biochemistry ¹	
 AST (SGOT) and ALT (SGPT) alkaline phosphatase Total bilirubin (if total bilirubin is $\geq 2x$ ULN (and no evidence of Gilbert's syndrome) then fractionate into direct and indirect bilirubin Gamma glutamyltransferase albumin creatinine Urea CRP Magnesium Potassium Bicarbonate sodium Calcium Chloride Total protein 	Prior to each infusion until off protocol therapy.
	
 TSH² 	one month after the first infusion
	
 INR/APTT 	As clinically indicated.
Radiology ⁴	
 CT scan chest and upper abdomen³ 	prior to surgery
	
 PET scan 	prior to surgery
Other Investigations	
 ECG urinalysis pregnancy test if applicable 	As clinically indicated.
	
 lung function tests: FEV1, FVC, TLCO⁴ and SaO2 on room air 	Only if pulmonary symptoms/suspicion of pneumonitis (see Section 7.5).
Correlatives	
 serum, plasma 	At the time of 3 rd infusion
Adverse Events	Patients must be evaluated after each cycle for adverse events	

1 **Bloodwork** Timing: Pre-treatment blood draws may be done the day prior to treatment if necessary, and when treatment is to begin on a Monday, may be done on the previous Friday (maximum 72 hours prior to treatment).

2 If TSH is abnormal, both T3 and T4 should be measured (both are recommended but at least one of T3 or T4 is mandatory if TSH is abnormal).

3 Must be contrast enhanced CT scan; low dose surveillance CT is not acceptable. To ensure comparability, the baseline scans and subsequent scans to assess response must be performed using identical techniques (i.e. scans performed immediately following bolus contrast administration using a standard volume of contrast, the identical contrast agent, and preferably the same scanner). When relapse is first documented at any site, complete restaging is required to identify all sites of relapse.

4 These exams should have been analysed before surgery by primary physician and surgeon to confirm the operability.

9.2 Evaluation after protocol treatment but prior to disease relapse/new invasive primary malignancy

The following investigations are to be performed for the period after discontinuation of durvalumab and surgery.

All patients must be seen at 4 weeks after surgery. Follow up visits then occur at 6 months and one year and then according to current guidelines.

	Investigations	Timing
Physical Exam including:	
 physical examination including blood pressure performance status Concomitant medication Adverse events 	Every follow up visit
Hematology	
 CBC including hemoglobin, differential, platelet count 	Only at 4 weeks after surgery. Thereafter as clinically indicated only or to follow durvalumab related AEs until resolution to grade 0-1.
Biochemistry	
 AST (SGOT) and ALT (SGPT) alkaline phosphatase Total bilirubin (if total bilirubin is $\geq 2x$ ULN (and no evidence of Gilbert's syndrome) then fractionate into direct and indirect bilirubin Gamma glutamyltransferase albumin creatinine Urea CRP Magnesium Potassium Bicarbonate sodium Calcium Chloride Total protein 	Only at 4 weeks after surgery. Thereafter as clinically indicated only or to follow durvalumab related AEs until resolution to grade 0-1.
	
 TSH¹ 	At 4 week after surgery and then as clinically indicated, or to follow durvalumab related AEs until resolution to grade 0-1. ²
	
 INR/APTT 	As clinically indicated.
Radiology ³	
 CT scan chest and upper abdomen³ other imaging as clinically indicated if suspicion of relapse or new primary invasive malignancy⁴ 	6 monthly for one year and then according to current guidelines.
Other Investigations	
 ECG 	4 weeks after surgery then as clinically indicated
	
 urinalysis pregnancy test if applicable 	As clinically indicated.
	
 lung function tests: FEV1, FVC, TLCO and SaO2 on room air 	Only if pulmonary symptoms or suspicion of pneumonitis (see Section 7.5 for full recommendations).

- 1 If TSH is abnormal, both T3 and T4 should be measured (both are recommended but at least one of T3 or T4 is mandatory if TSH is abnormal).
- 2 TSH may be completed within 7 days prior to visit.
- 3 Must be contrast enhanced CT scan, low dose surveillance CT is not acceptable. To ensure comparability, the baseline scans and subsequent scans to assess response must be performed using identical techniques (i.e. scans performed immediately following bolus contrast administration using a standard volume of contrast, the identical contrast agent, and preferably the same scanner).
- 4 When relapse is first documented at any site, complete restaging is required to identify all sites of relapse.

9.3 Evaluation after disease relapse or new invasive primary malignancy (during or after protocol treatment)

Should a patient relapse or develop a new invasive primary malignancy (as defined in Section 10) during the trial, details should be entered in the EDC disease event form and patient follow-up will be altered. All study patients must have a visit 4 weeks, 6 months and one year after surgery.

Treatments received by the patient after relapse and for new primary malignancies will be left to the discretion of the patient and his/her physician, but all treatments will be recorded in the EDC case report forms. All sites of NSCLC relapse or new primary malignancies will be recorded on the case report forms.

Follow up visit according to the centre practice.

Investigations		Timing
Physical Exam including:	
 • subsequent anti-cancer therapy • physical examination including pulse, blood pressure • performance status 	Every follow up visit.
Hematology	
 • CBC including hemoglobin, differential, platelet count 	Only at 4 week post surgery. Thereafter as clinically indicated only or to follow durvalumab related AEs until resolution to grade 0-1.
Biochemistry	
 • AST (SGOT) and ALT (SGPT) • alkaline phosphatase • bilirubin • creatinine 	Only at 4 week post surgery. Thereafter as clinically indicated only or to follow durvalumab related AEs until resolution to grade 0-1.
	
 • TSH¹ 	At 4 week and then as clinically indicated, or to follow durvalumab related AEs until resolution to grade 0-1. ²
	
 • INR/APTT 	As clinically indicated.
Radiology	
 • CT scan chest and upper abdomen • other imaging as clinically indicated if suspicion of relapse or new primary invasive malignancy 	According to current guidelines.
Other Investigations	
 • ECG • urinalysis • pregnancy test if applicable 	As clinically indicated.
	
 • Lung function tests: FEV1, FVC, TLCO and SaO2 at room atmosphere 	Repeat if pulmonary symptoms/suspicion of pneumonitis.
Adverse Events	Patients must be evaluated for durvalumab related adverse events at each visit, including late events.	

1 If TSH is abnormal, both T3 and T4 should be measured (both are recommended but at least one of T3 or T4 is mandatory if TSH is abnormal).

2 TSH may be completed within 7 days prior to scheduled visit.

10 SURGERY AND PATHOLOGICAL ASSESSMENT

10.1 Surgery

After durvalumab administration and prior to surgery, a second PET scan as well as a second thorax CT scan must be done to evaluate Response to durvalumab treatment.

We plan only three infusions of PD-L1 antibody (one infusion every two weeks) with a schedule allowing surgery to be performed not later than 6 weeks after first infusion. Surgery will be performed between 2 days and 2 weeks after the last infusion.

Before surgery, all adverse events must recover to a grade ≤ 1 .

Surgery may consist of lobectomy, sleeve resection, bilobectomy or pneumonectomy as determined by the attending surgeon based on the intraoperative findings. Patients who have had only segmentectomies or wedge resections are not eligible for this study. Resection may be accomplished by open or VATS techniques.

Lymph node mapping is defined by The International Association for the Study of Lung Cancer (IASLC) lymph node map. The nodal tissue must be labelled according to the recommendations of the American Thoracic Society. Surgeons are encouraged to dissect or sample all accessible nodal levels in accordance with the European Society of Thoracic Surgeons guidelines. Accordingly, a minimum of three lobe specific mediastinal nodal stations (N2), one of which must include station 7, and at least one N1 station - inclusive of the ones removed with the pulmonary specimen - must have been sampled at the end of the procedure.

Description of surgical resection (complete or not) is mandatory (see section 10).

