15.2 Sample Size, Power

The maximum sample size (N) is calculated based on α , β , and the expected effect size, using a test for single binomial proportion for a two-stage design with a 1:1 randomization and O'Brien-Fleming (OF) stopping rules, allowing for early stopping for futility after Stage I. The software East 6.0 was used.

The rate of complete resection equal to or lower than 85% (P0) is considered as unacceptable after immune treatment. On the other hand, we can conclude to a good rate of complete resection if it is 95% (P1). The computation is based on the following assumption, considering the probability of compliance: P0 =85%; P1 = 95%; statistical power of 0.90; type I error rate (one-sided) of 0.05.

The null hypothesis that the rate of complete resection is P0 = 85% will be tested against a one-sided alternative. In the first stage, 39 patients will be accrued. If there are 34 or fewer responses in these 39 patients, the study will be stopped for futility. Otherwise, 38 additional patients will be accrued for a total of 77. The null hypothesis will be rejected if 71 or more responses are observed in 77 patients. To take into account 5% of ineligible patients, 81 patients will be included.

Duration of accrual: 18 months and 1 year follow-up.

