15.3 Analysis population

- The population of tolerance is defined as all patients who received one dose of treatment

- The population the intent to treat (ITT) will include all patients included
- The population of eligible patients will consist of ITT patients presenting no deviation judged major on the criteria for inclusion and non-inclusion

The deviations to the protocol will be reviewed by the principal investigators and then classified into minor or major deviations, and listed.

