15.4 Study Endpoints and Analysis

The primary endpoint will be performed on all eligible patients based on patient percentage surgical resection R0 after a maximum of 3 cycles of chemotherapy. It will be presented associated with confidence interval of 95%.

DFS is a secondary endpoint, defined as the time from the date of inclusion to the date of first documented disease relapse or the occurrence of a new invasive primary malignancy or death from any cause. Patients who are alive and disease/new invasive primary malignancy-free at the time of each analysis will be censored at their last disease assessment date.

OS is a secondary endpoint, defined as the time from the inclusion to the date of death of any cause, or censored at their last known alive date. All analysis on DFS will be carried out for the OS endpoint.

The analysis of secondary endpoints will be performed on patient eligible.

Although PD-L1 expression as measured by immunohistochemistry is hypothesized to be a potential predictive marker, this is as yet not validated in either the adjuvant or palliative settings. Further, the cut-off defining PD-L1 positivity has not been validated. This trial will also explore the utility of PD-L1 as a predictive biomarker as well as the optimal cut-off for positivity.

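### Section 10.1 makes eligibility depend on the operation performed after durvalumab, in conflict with the eligible population that Sections 15.3 and 15.4 use for the primary R0 rate

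*Protocol*

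**What the plan says.** Section 10.1 places surgery between 2 days and 2 weeks after the last infusion. It lists the forms that surgery may take, with the choice made "as determined by the attending surgeon based on the intraoperative findings". The next sentence reads: "Patients who have had only segmentectomies or wedge resections are not eligible for this study".

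Section 5.1 applies eligibility requirements at the time of inclusion. Neither 5.1 nor 5.2 contains a criterion on the type of operation.

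Section 15.3 states: "The population of eligible patients will consist of ITT patients presenting no deviation judged major on the criteria for inclusion and non-inclusion". It adds: "The deviations to the protocol will be reviewed by the principal investigators and then classified into minor or major deviations, and listed".

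Section 15.4 states: "The primary endpoint will be performed on all eligible patients based on patient percentage surgical resection R0". On the other endpoints: "The analysis of secondary endpoints will be performed on patient eligible".

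Section 15.2 sets the decision rule and the allowance: "The null hypothesis will be rejected if 71 or more responses are observed in 77 patients", and "To take into account 5% of ineligible patients, 81 patients will be included".

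**The concern.** The protocol uses the word eligible in two incompatible ways, and that word decides the primary denominator. Under Section 15.3 it is a baseline property. Under Section 10.1 it also depends on what the surgeon did after treatment.

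If Section 10.1 is followed, a patient who received durvalumab and then had only a segmentectomy or wedge resection leaves the primary analysis because of an event at surgery, which is the very step the primary endpoint assesses. The same patient leaves DFS and OS, both counted from inclusion. The trial is unblinded and the principal investigators classify deviations, so the removal could be decided with the resection result known. Table 1 of the protocol calculates its historical resection rates over all patients included in the neoadjuvant arm, so the removal would also depart from the basis of the benchmark.

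The reach is limited. Section 10.1 does not remove unoperated patients, exploratory thoracotomies, or anatomical resections with R1 or R2 margins.

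**Working it through.** **Inputs from the protocol (Section 15.2).** P0 = 0.85; P1 = 0.95; one-sided type I error 0.05; power 0.90. Stage 1: stop if 34 or fewer of 39 are complete. Final: reject if 71 or more of 77 are complete. 81 patients are included to allow for 5% ineligible.

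**Reproducing the plan.** P(reject | p) = sum over x = 35 to 39 of Bin(x; 39, p) × P(Bin(38, p) ≥ 71 − x).
- p = 0.85: 0.0423, within the stated 0.05.
- p = 0.95: 0.8949, in line with the stated 0.90.
- Allowance: 77 × 1.05 = 80.85, rounded to 81.

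The rule and sample size are not in question.

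**Effect of removal.** The protocol gives neither the number of sublobar-only operations nor their R0 rate, so both are assumptions. Let k of the 81 be removed, a share q of them R0, and let p be the complete-resection rate among all patients. The rate among those analysed is

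p* = (81p − kq) / (81 − k).

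Example, k = 2, q = 0.5, p = 0.85: (68.85 − 1)/79 = 0.8589. Putting p* into the two-stage formula, on the assumption that 77 patients are analysed, gives these false-positive rates at p = 0.85:

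| Share R0 among removed | k = 1 | k = 2 | k = 4 |
|---|---|---|---|
| 100% | 0.039 | 0.035 | 0.029 |
| 85% | 0.042 | 0.042 | 0.042 |
| 50% | 0.052 | 0.064 | 0.098 |
| 0% | 0.070 | 0.112 | 0.266 |

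Four removals use the whole ineligibility allowance (81 − 77 = 4), so the 0.266 cell is an extreme corner. In the other direction, at p = 0.95 with all removed patients R0, power falls from 0.895 to 0.890, 0.885 and 0.874 for k = 1, 2 and 4.

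**At the cut-off itself** (exact 95% intervals):
- As stated: 71/77 = 92.2% (83.8 to 97.1).
- One removed patient kept: 71/78 = 91.0% (82.4 to 96.3) if not complete, 72/78 = 92.3% (84.0 to 97.1) if complete.
- Four removed patients kept: from 71/81 = 87.7% (78.5 to 93.9) to 75/81 = 92.6% (84.6 to 97.2).

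The figures over 78 and 81 are descriptive only, because the protocol gives a cut-off for 77 alone.

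**The case against.** The strongest reply is that the analysis set is already fixed. Section 15.3 removes patients only for major deviations on inclusion or non-inclusion criteria, those lists name no operation, and Section 10.1 does not mention an analysis population. A departure from Section 10.1, even if graded major, does not meet the wording of Section 15.3. Deviations are also to be listed, so a removal would be visible.

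The sentence may be left over from a design in which surgery precedes enrolment. Section 7 similarly expects post-operative change on the baseline CT, and Section 15.4 refers to cycles of chemotherapy. Finally, the numbers rest on assumed counts, the direction is unknown, and nothing changes if the removed patients have the average R0 rate.

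Most of this stands. Section 15.3 is the better reading, the wording may well be carried over, and the magnitude is hypothetical. But the conflicting sentence remains under trial surgery and tells whoever classifies deviations, in writing, that such a patient is not eligible. If it was meant for surgery before inclusion, it belongs in Section 5 and is absent there. It needs correcting on either reading.

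**Conclusion.** The concern holds. As written, Section 10.1 makes eligibility depend on a post-treatment event, while Sections 5.1 and 15.3 tie it to inclusion and Section 15.4 builds the primary denominator on it. This is a contradiction in the text, not detail left for an analysis plan.

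If Section 15.3 is followed, the primary result is unaffected. If Section 10.1 is followed, dropping an R0 sublobar case lowers the observed rate and dropping a non-complete one raises it, so neither the sign nor the size of the bias can be known from the protocol. Under the assumed counts, the effect is small for one patient (false-positive rate 0.039 to 0.070 against 0.042). With two removed, the rate exceeds the nominal 0.05 if half or fewer are R0. It should be fixed, but it does not undermine the design.

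**What to change.** In Section 10.1, replace the eligibility wording with a statement that the type of operation performed does not change a patient's analysis population. In Sections 15.3 and 15.4, add that no patient is removed from the primary population because of the operation performed or its result. Sublobar-only patients then stay in the denominator.

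To classify them, one definition of complete resection is needed. Section 1.2 requires a nodal dissection and a negative highest mediastinal node, while Section 11.1.1 requires only gross removal and negative margins. These two should be reconciled. The correction to the population can go ahead without waiting for that. A sensitivity analysis counting sublobar-only patients as not complete is optional. No view is taken here on which operation is appropriate.

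The cost is amendment wording in Section 10.1, one sentence in Sections 15.3 and 15.4, and agreement on the endpoint definition. The sample size and cut-offs stay as they are. The reported R0 rate may come out slightly lower or higher than with these patients removed.

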10.2 Pathological assessment

A standard approach to post neoadjuvant therapy pathologic assessment is required to use pathological complete response as a demonstration of treatment efficacy. This requires a multidisciplinary communication and information on the pre-treatment tumor size and location, pre-treatment cTNM and evaluation of the clinical response on tumor and mediastinal nodes, critical for the pathologist to perform adequate sampling of the presumed tumor bed and immediately adjacent tissue. Residual tumor is often softer and tumor size and extent is difficult to assess after neoadjuvant therapy. The pathologist must also be informed of the clinical trial and histological type of the pretreatment biopsy.

This standard approach include a precise macroscopic description of the surgically resected NSCLC with macroscopic size in two dimensions of the largest cross section, location of the tumor and distance to close margin i.e. pleural surface and bronchial sleeve resection. Extent of macroscopic necrosis for tumor and node must be reported with semi quantitative assessment. Diagram (or images of the sliced resection) is useful to annotate the tissue section. The number of blocks sampled in the tumor area must be reported.

10.3 Surgical snap frozen tissue and paraffin embedded block

Paraffin embedded blocks must be available. Frozen Tissue (one block for tumor and nodes, only collected if there is grossly obvious residual invasive cancer on macroscopic examination), fresh tumor (and if available metastatic lymph nodes) and normal tissue will be collected if available. Local policy must permit the submission of tissue blocks. Tissue blocks from the surgically resected NSCLC must be submitted for:

-pathological examination with at least one slide assessed by cm of tumor in the greatest diameter as well as each removed lymph node

- PD-L1 assessment on paraffin tissue
- Other biomarkers
- Study of the immune reactivity of tumors in response to immunotherapy

11 CRITERIA FOR MEASUREMENT OF STUDY ENDPOINTS

11.1 Definitions

11.1.1 Complete resection

All gross disease must have been removed at the end of surgery. All surgical margins of resection must be negative for tumour.

Margins are classified by the pathologist as:

R0 - no cancerous cells seen microscopically; this is the desired result

R1 - cancerous cells can be seen microscopically

R2 - even gross examination by the naked eye shows tumor tissue on the margin, indicating more remains on the patient.

